10.0 EFFICACY ANALYSES

The efficacy analyses will be based on the ITT Population. All summaries on this population will be based on the investigational product each subject was randomized to receive. The multiple imputation (MI) approach will be used to impute missing values for co-primary and secondary efficacy analyses and details are further described in Section 16.2. Sensitivity analyses for efficacy parameters will be performed using alternative approaches to handle missing data, as well as an observed cases (OC) approach using the PP population. *Baseline* for efficacy is defined as the last non-missing efficacy assessment before the first dose of the investigational product. All statistical tests will be 2-sided hypothesis tests performed at the 5% level of significance for main effects. All confidence intervals will be 2-sided 95% confidence intervals, unless stated otherwise.

The descriptive statistics for all the continuous variables will include the mean, median, 25th percentile, 75th percentile, standard deviation (SD), standard error of mean (SEM), minimum, maximum, and number of subjects. Descriptive summaries will be provided for raw, change from baseline (CFB), and %CFB values for continuous efficacy endpoints. Frequency distributions for all the categorical variables will be presented as counts and percentages. Summaries will be provided by visit and treatment, as appropriate.

While every effort will be made to randomize a sufficient number of subjects at each study site, in the event that this is not possible, study sites may be pooled for statistical inference testing. Study sites (centers) will be pooled by geographical location based on region definitions from the US Census Bureau (Northeast, Midwest, South, and West; US Census Bureau, 2013) for analysis purposes so that in each pooled site the number of subjects is reasonably large and consistent in size between pooled sites. Sites within a geographic location will be pooled starting with the sites that have the lowest number of randomized subjects pooled together such that the pooled site has a minimum of 12 randomized subjects after pooling.

The sites to be pooled for each geographic location will be documented in a signed memo prior to unblinding of the treatment code. A list of sites and the corresponding pooled sites will be presented.

10.1 CO-PRIMARY EFFICACY PARAMETERS

There will be two co-primary efficacy parameters (endpoints) for this study. The first co-primary efficacy endpoint will be the absolute CFB in inflammatory lesion counts at Week 12. This variable will be considered a continuous variable. The second co-primary efficacy endpoint will be IGA success at Week 12. IGA success will be a dichotomous variable defined as at least 2-point decrease from baseline on the IGA assessment as well as a score of clear (0) or almost clear (1) on the IGA assessment.

10.1.1 CFB in Inflammatory Lesion Counts

The co-primary endpoint, absolute CFB in inflammatory lesion counts at Week 12, will be analyzed using an analysis of covariance (ANCOVA) model with the baseline value as a covariate and additional terms included to represent effects of treatment and (pooled) site. The primary efficacy analysis will be based on the ITT population. Missing data will be imputed using an MI approach further described in Section 16.2. The adjusted means with associated 95% confidence intervals (CIs) from the ANCOVA model will also be presented for each treatment and for the difference between the treatments.

Statistical significance between the treatments, sarecycline compared to placebo, will be declared if the p-value of the hypothesis test from the ANCOVA model is less than or equal to 0.05. The ANCOVA model will be performed using SAS® PROC MIXED with the methodology of Littell et al. (2006).

Let X_{ijk} and Y_{ijk} be the baseline and endpoint values for the k th subject in the j th site and the i th treatment, where $k=1, \dots, n_j$, $j=1, \dots, c$ (the number of sites after pooling, if applicable) and $i=\text{sarecycline, placebo}$. Then

$$Y_{ijk} - X_{ijk} = \mu + \tau_i + \gamma_j + \beta X_{ijk} + \varepsilon_{ijk}$$

where μ is the overall mean, τ is the fixed effect of the i th treatment, γ is the fixed effect of the j th site, β is a regression coefficient for baseline and ε_{ijk} is the $\text{NID}(0, \sigma^2)$ random error component. Hypothesis tests for the active treatment effect of sarecycline compared to placebo will be conducted using differences of adjusted means.

As site is included in the primary ANCOVA model, a treatment-by-site interaction will be investigated as an exploratory analysis to assess the homogeneity of treatment effects across site. This effect will be investigated analytically prior to any pooling of sites by adding the interaction term to the ANCOVA model and testing for significance. Because interactions are not powered in this study, testing for significance will be at the 0.10 level. However, any significant interaction findings at the 0.10 level will also take into account the potential for spurious results. Further exploration may be done graphically with interaction plots to determine the nature of the interaction and to identify any “outlier” sites with attention focused on qualitative differences in treatment effects. If large differences in treatment effects are seen in any “extreme” sites, then sensitivity analyses will be performed that exclude sites with the highest extreme treatment effect values from the analysis. Any such sites may be further investigated for explanation involving study conduct, subject demographics, current medications, etc.

In addition, the following sensitivity analyses will be performed:

- Inflammatory lesion count data will be analyzed for CFB at Week 12 according to an ANCOVA model with the baseline value as a covariate and effects of treatment and (pooled) site using the PP population with OC data.

- LOCF will be used as an imputation method for cases where the Week 12 CFB in inflammatory lesion counts value is missing. The endpoint will then be analyzed according to an ANCOVA model with the baseline value as a covariate and effects of treatment and (pooled) site.
- Baseline observation carried forward will be used as an imputation method for cases where the Week 12 CFB in inflammatory lesion counts value is missing. The endpoint will then be analyzed according to an ANCOVA model with the baseline value as a covariate and effects of treatment and (pooled) site.
- Mixed model repeated measures (MMRM) analysis will be used to explore the sensitivity of data handling for CFB in inflammatory lesion counts for subjects who withdraw from the study. The model will include the fixed effects of treatment, pooled site, and visit, the baseline value as a covariate, and the treatment-by-visit interaction term. An unstructured covariance matrix will be used initially in the model for the correlation pattern among the repeated measures. If this does not converge, then the Toeplitz covariance structure (TYPE=TOEP in SAS MIXED procedure) will be used instead. If the results from the MMRM analyses differ qualitatively with the results from the primary efficacy analysis, further analyses will be performed to investigate the causes of the difference. However, the results from the primary efficacy analysis will be considered the primary efficacy results.
- A rank transformation will be applied to each of the multiple datasets created from the MI approach and the analysis will proceed for Week 12 using an ANCOVA model on the ranks with the baseline value as a covariate and effects of treatment and (pooled) site. Tied values will receive the mean value (midranks) of the corresponding ranks.

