These endpoints will be analyzed for each visit using an analysis of covariance (ANCOVA) model with terms included to represent effects of treatment and (pooled) site and the baseline values as a covariate for the ITT population. Missing data will be imputed using an MI approach, as described in Appendix 16.2. The adjusted means with associated 95% CIs for the ANCOVA model will also be presented for each treatment and for the difference between the treatments. Statistical significance between the treatments, sarecycline compared to placebo, will be declared if the p-value of the hypothesis test from the ANCOVA model is less than or equal to 0.05.

For the Week 12 percent CFB analysis, as site is included in the ANCOVA model, a treatment-by-site interaction will be investigated as an exploratory analysis to assess the homogeneity of treatment effects across site. This effect will be investigated analytically by adding the interaction term to the ANCOVA model and testing for significance. Because interactions are not powered in this study, testing for significance will be at the 0.10 level. However, any significant interaction findings at the 0.10 level will also take into account the potential for spurious results with attention focused on qualitative differences in treatment effects. If large differences in treatment effects are seen in any “extreme” sites, then sensitivity analyses will be performed that exclude sites with the highest extreme treatment effect values from the analysis. Further exploration may be done graphically with interaction plots to determine the nature of the interaction and to identify any “outlier” sites. Any such sites may be further investigated for explanation involving study conduct, subject demographics, current medications, etc.

An additional exploratory analysis will be done for the percent CFB analysis by visit. A rank transformation will be applied to each of the multiple datasets created from the MI approach and the analysis will proceed using an ANCOVA model on the ranks with the baseline value as a covariate and effects of treatment and (pooled) site. Tied values will receive the mean value (midranks) of the corresponding ranks.

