13.0 INTERIM ANALYSIS

No interim analysis is planned for this study.

14.0**DETERMINATION OF SAMPLE SIZE**

The sample size was selected to provide an adequate number of subjects to compare the efficacy of sarecycline treatment to placebo and to provide an adequate number of subjects needed for a safety database.

Sample size estimates were calculated for each of the co-primary efficacy endpoints, absolute CFB in facial inflammatory lesion counts and facial IGA success (based on at least 2-point decrease from baseline in IGA score), and the first secondary efficacy endpoint, percent CFB in facial inflammatory lesion counts at Week 12 last observation carried forward (LOCF). The results from a recent study (Study PR-10411) of sarecycline compared to placebo treatment were used to estimate the sample size needed to show a significant difference between the treatments at $\alpha=0.05$ and 90% power using two-sided tests and a 1:1 randomization. It should be noted that one outlier in the data for Study PR-10411 was removed from the estimate for absolute CFB in inflammatory lesion counts in order to provide more accurate estimates for the sample size determination. Results of the calculations and the estimates used in the calculations are provided below:

Continuous Endpoints^a	Sarecycline CFB or %CFB	Placebo CFB or %CFB	Common SD	Sample per Treatment	Total Sample Size
Absolute CFB in inflammatory lesion counts (co-primary)	16	13	12	338	676
Percent CFB in inflammatory lesion counts (secondary)	52%	39%	41%	210	420

a Sample size was based on a two sample t-test of no difference between the treatments

Dichotomous Endpoints^a	Sarecycline Rate	Placebo Rate	Difference in Rates	Sample per Treatment	Total Sample Size
IGA Success (2-point decrease in IGA score from baseline and a score of clear/almost clear; co-primary)	23%	10%	13%	170	340

a Sample size was based on a χ^2 test of no difference between the proportions

While the IGA scale proposed for the Phase 2 study is slightly different than the IGA scale in the Phase 2, the number of subjects to be enrolled (500 per treatment; 1000 total) should provide more than sufficient power for the efficacy evaluations. Additionally, a larger sample is needed in order to provide sufficient numbers of subjects on sarecycline treatment for a safety database.

15.0**STATISTICAL SOFTWARE**

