- For inflammatory lesion counts, if any of the subtypes (papules, pustules, and nodules/cysts) is missing, the inflammatory lesion count is missing. The variables included in the imputations are age, gender, and the measurements of the corresponding endpoint count) at baseline, Week 3, Week 6, Week 9, and Week 12.
- For IGA, the raw scores will be used for the imputation. The variables included in the imputations are age, gender, and the measurements of the endpoint at baseline, Week 3, Week 6, Week 9, and Week 12.
- All imputations will be performed by treatment group based on the randomized study medication and based on the randomized gender strata. The number of imputation is set at 20 with number of 50 burn-in iterations. The seed used for imputation for all endpoints is [REDACTED]. The logistic regression model for gender is based on the probability of female. For age, IGA raw scores and lesion counts, regression with predictive mean matching method will be used. The imputed values will be rounded to the nearest integer for IGA and lesion counts.
- The following are the SAS programs used to impute IGA at week 12:

The following SAS program will be used to impute inflammatory and non-inflammatory lesion counts at week 12.

- An analysis of covariance (ANCOVA) model for inflammatory lesion counts and a CMH analysis for the IGA success as stated in Sections 10.1.1 and 10.1.2, respectively, will be performed for each of the imputed dataset.
- An analysis of covariance (ANCOVA) model for inflammatory and non-inflammatory lesion counts as stated in Section 10.2 will be performed for the imputed dataset for the secondary endpoints.
- The SAS PROC MIANALYZE procedure will be used to produce final parameter estimates, including the point estimates and standard errors, adjusted treatment differences, confidence intervals and p-values for the primary and secondary variables.
- For the CMH test, the Wilson-Hilferty transformation (Wilson & Hilferty, 1931, O'Kelly & Ratitch, 2014) will be used. Under the null hypothesis, the transformed statistic is approximately normally distributed:

$$wh_CMH^{(m)} = \sqrt[3]{\frac{cmh^{(m)}}{k}} \sim normal\left(1 - \frac{2}{9k}, \frac{2}{9k}\right)$$

Where $cmh^{(m)}$ is the chi-square statistics each with k degrees of freedom from $m = 1, \dots, M$ imputed datasets. In this case, $k=1$. This statistic will be passed to PROC MIANALYZE to obtain the combined p-value for CMH test.

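### SAP 16.2 implies that randomisation was stratified by gender, Protocol 9.4.3 names no stratum, and the lesion-count models omit gender; settling this and adding one term would bring a small gain in precision

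*SAP*

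**What the plan says.** **Randomisation.** Protocol 9.4.3 specifies 1:1 block randomisation through the IRT and names no stratification factor. The study description in SAP 4.0 names none either. The only mention of strata is in the imputation rules of SAP 16.2, which run by treatment group "based on the randomized study medication and based on the randomized gender strata". The matching rule in Protocol 11.4.3 imputes by treatment group only. SAP 16.2 also lists gender among the imputation variables and gives it its own logistic imputation model.

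**Analysis models.** The co-primary ANCOVA (SAP 10.1.1; Protocol 11.5.1) is fitted "with the baseline value as a covariate and additional terms included to represent effects of treatment and (pooled) site". The secondary ANCOVA (SAP 10.2; Protocol 11.5.3) is fitted "with terms included to represent effects of treatment and (pooled) site and the baseline values as a covariate". The ANCOVA sensitivity analyses use the same terms, and the MMRM adds visit and treatment-by-visit. The co-primary IGA analysis (SAP 10.1.2) is a CMH test adjusted for (pooled) site. None includes gender, which appears only in the imputation and as a subgroup for summaries.

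**The concern.** When randomisation is balanced within a factor, the design removes that factor's variation from the treatment contrast. A model that omits the factor still counts that variation as error, so the reported standard error exceeds the true sampling variation of the estimate. Tests are then slightly conservative and intervals slightly wide. If the factor was not a stratum, omitting it leaves the standard error valid, but a prognostic covariate goes unused. These are two different effects, and which one applies depends on a fact on which the two documents disagree.

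The ANCOVA p-values decide one of the two co-primary endpoints. They also decide all the secondary tests in SAP 10.2: 1 (percent change, inflammatory, Week 12) + 6 (absolute and percent, inflammatory, Weeks 9, 6, 3) + 8 (absolute and percent, noninflammatory, four visits) = 15. These run in a fixed sequence at 0.05. Only the first of the 15 has a stated sample size.

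**Working it through.** **Inputs from the documents.** Two-sided 5% tests (SAP 10.0: "All statistical tests will be 2-sided hypothesis tests performed at the 5% level of significance for main effects"); SAP 14.0: "and 90% power using two-sided tests and a 1:1 randomization"; the co-primary row, "Absolute CFB in inflammatory lesion counts (co-primary) 16 13 12 338 676"; 500 per arm enrolled.

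**Reproducing the plan's figures.** For a difference of 16 − 13 = 3 and SD 12, the normal approximation gives 337 per arm and the noncentral t gives 338, as stated. Percent change (13 points, SD 41) gives 210. IGA success (23% v 10%, pooled chi-square) gives 170. All three agree with SAP 14.0.

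**Assumption.** Let R² be the share of residual variance that gender explains after baseline and site. Neither document gives a gender effect, so R² is varied: 0, 1%, 3%, 5%. With equal numbers of each gender (also assumed) and SD 12, the implied male–female difference in change is 24√R², or 2.4, 4.2 and 5.4 lesions at 1%, 3% and 5%.

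**Formulas, at 500 per arm.**
- SE without gender: SE₀ = 12·√(2/500) = 0.759, and 3/SE₀ = 3.953.
- SE with gender: SE₀·√(1−R²).
- Stratified, gender omitted: SE ratio = 1/√(1−R²); size = 2·[1 − Φ(1.96/√(1−R²))]; power = Φ[(3.953 − 1.96)/√(1−R²)].
- Unstratified, gender omitted: size 5%; power = Φ(3.953 − 1.96) = 97.7%.
- Gender included: power = Φ[3.953/√(1−R²) − 1.96].
- Subjects lost, unstratified: 1000·R².
- Subjects lost, stratified: 1000·(1 − r²), with r = [1.96 + 1.993/√(1−R²)] / [3.953/√(1−R²)], the sample fraction at which the gender-adjusted test has the same power.

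| R² | SE with gender | SE₀ excess | Size if stratified | Power: stratified, omitted | Power: unstratified, omitted | Power: gender included | Subjects lost: stratified | Subjects lost: unstratified |
|---|---|---|---|---|---|---|---|---|
| 0 | 0.759 | 0 | 5.0% | 97.69% | 97.69% | 97.69% | 0 | 0 |
| 1% | 0.755 | 0.5% | 4.9% | 97.74% | 97.69% | 97.79% | 5 | 10 |
| 3% | 0.747 | 1.5% | 4.7% | 97.85% | 97.69% | 98.00% | 15 | 30 |
| 5% | 0.740 | 2.6% | 4.4% | 97.96% | 97.69% | 98.19% | 25 | 50 |

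In the stratified column the loss is half the unstratified one, because the estimate already benefits from the balance and only the yardstick is too long. The largest gain from adding gender is 98.19 − 97.96, about 0.24 points, if stratified, and 98.19 − 97.69, about 0.5 points, if not.

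**Simulation check** (4000 trials per scenario; assumed 40 pooled sites of 25, half female, blocks of 4; R² = 5%). Stratified, gender omitted: mean reported SE 0.761 against an empirical SD of 0.732, type I error 0.040. Unstratified: 0.760 against 0.760, type I error 0.051. Monte Carlo error of the empirical SD is about 1%, so this confirms the direction and the contrast between the cases, not the second decimal of the size.

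**The case against.** A reader might infer that the lesion-count standard errors are too wide as a matter of fact. The documents do not support that. It needs gender to have been a stratum and to be prognostic after baseline and site, and neither is established. The stratum rests on one phrase in SAP 16.2, and that section's logistic model for gender fits poorly with imputing within gender. The SAS code that might settle it is not in the text available. This part of the objection stands, and it is why every figure above is conditional.

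A reader might also put the sub-5% size and the loss of 10, 30 or 50 subjects together. They belong to different cases: reduced size arises only with stratification, and the larger loss only without it.

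Three further points limit the finding without removing it:
- **Materiality.** The co-primary endpoint needs 676 subjects and 1000 are planned. Power is already about 98%, and any error is in the conservative direction. This is correct for Week 12 absolute change, but 14 of the 15 secondary tests have no stated power.
- **Preference.** Without stratification, the case for gender is the ordinary case for a prognostic covariate, and the prespecified model is valid. True; what then remains is an option that is cheap to take.
- **Protocol departure.** The ANCOVA terms are fixed in Protocol 11.5.1 and 11.5.3, and SAP 17.0 says the Protocol will not be amended for Amendment 1, written after all subjects had finished. Adding a term therefore has to be recorded as a departure, and done blind.

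**Conclusion.** The Protocol and SAP disagree on whether gender was a randomisation stratum, and no lesion-count model includes it. The consequence is minor and conditional. With stratification and R² of 1% to 5%, reported standard errors are 0.5% to 2.6% too wide and the loss is about 5 to 25 subjects. Without stratification the standard errors are valid and the loss is about 10 to 50 subjects of efficiency. With R² = 0 nothing is lost either way. There is no inflation of type I error and no threat to validity. The range for R² is an assumption; so is the use of the SAP 14.0 SD of 12 as the residual SD before gender is added. Adding gender is a free improvement with a small gain, not the correction of an error in the primary analysis.

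**What to change.** 1. Confirm the stratification factors from the randomisation specification, and reconcile Protocol 9.4.3, Protocol 11.4.3 and SAP 16.2. If gender was not a stratum, delete the reference to gender strata from SAP 16.2.
2. Before unblinding, add gender as a fixed factor to the ANCOVA models in SAP 10.1.1 and 10.2, and to the ANCOVA and MMRM sensitivity analyses of the same endpoints. Record this in the SAP as a departure from the model in Protocol 11.5.1 and 11.5.3.
3. Leave the IGA CMH strata at (pooled) site and say why. A pooled site may hold only 12 subjects; crossing with gender would leave about 6 per stratum if half are female, or about 3 per arm.

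Cost: one model term in the SAP and programs, and 1 of about 950 error degrees of freedom (1000 subjects less about 50 site, treatment and baseline parameters). Gender is already in the imputation model, so no new data are needed.

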10.1.2 IGA Success

The co-primary efficacy endpoint, percentage of subjects with IGA success at Week 12, will be analyzed for the ITT population using the CMH test with adjustment for (pooled) site. Missing data will be imputed using an MI approach further described in Section 16.2. The rate difference and the 95% CIs for the rate difference and the relative rate and the 95% CIs for the relative rate will be presented as well. The CI for the treatment rate difference will be based on two-sided 95% Wald type CIs with CMH weights (Kim & Won, 2013, Yan & Su, 2010).

The homogeneity of treatment effects across (pooled) site will be investigated as an exploratory analysis using the Breslow-Day test. If the Breslow-Day test indicates large heterogeneity in the odds ratios across (pooled) site, then further exploration may be done graphically or with further investigation for explanation involving study conduct, subject demographics, current medications, etc.

In addition, the following sensitivity analyses will be performed:

- IGA success at Week 12 will be analyzed using a CMH test with adjustment for (pooled) site on the PP population with OC data.
- For IGA success, subjects who discontinue from the study early will be coded as failures for the Week 12 analysis. A sensitivity analysis of IGA success using this data handling convention will be performed using a CMH test with adjustment for (pooled) site.
- For IGA success, subjects who discontinue from the study early will be coded as failures for subjects on sarecycline and successes for subjects on placebo. A sensitivity analysis of IGA success using this data handling convention will be performed using a CMH test with adjustment for (pooled) site.

